### Sample Size Determination / Power Analysis

The primary foci of this study are amount of breast milk expressed after initiation and time to lactogenesis II. For the continuous longitudinal outcome amount of breast milk expressed, with 60 subjects randomized to each intervention group (early, intermediate, late initiation), we will have 85% power to detect at least a 0.5 standardized (sd units) effect size between the three intervention groups [assuming 13 time points (initial expression, days 1-7, 14, 21, 28, 35, 42)]; intra-class correlation no greater than 0.5; level of significance ( $\alpha$ )=0.02, two-tailed ]. A standardized effect size of 0.49sd (Cohen's d, "moderate" effect) is equivalent to a raw effect size of 125 ml (raw scale units) for expressed breast milk (assuming pooled sd for expressed breast milk is 250, from preliminary data. For number of hours to achieve lactogenesis II assuming  $\alpha$  = 0.02 (Type I error rate), two-sided; independent sample t-test comparison of means (adjusted for multiple comparison between 3 groups); equality of variance between groups with 60 mothers per group we will have 85% power to detect a difference of 34.1 hours (effect size  $\Delta$ =0.62s;  $s$ =55.0) between the groups.

For analysis of the continuous secondary efficacy outcome measure self-efficacy, we will have 85% power to detect a difference of 0.62 s between the three groups assuming  $\alpha$  = 0.02 (Type I error rate), two sided; independent sample t-test comparison of means; equality of variance between groups accounting for multiple comparisons.

### Randomization

Table 1. Randomization and Stratification of Mothers

Gestational Age	Group 1 Early Expressers	Group 2 Intermediate Expressers	Group 3 Late Expressers
23-27 weeks	0-60 minutes	61-180 minutes	181-360 minutes
28-32 weeks	0-60 minutes	61-180 minutes	181-360 minutes

mothers into groups. Following the birth of an infant weighing less than 1500 grams, with a gestational age between 23-32 weeks, mothers who continue to meet inclusion criteria will be stratified according to the gestational age of the infant (23-27 weeks and 28-32 weeks). Gestational age will be determined through one of the following; 1st or 2nd trimester ultrasound or the average of the obstetric gestational age and the results of the Ballard exam. This stratification is based upon likely differences in breast milk production in mothers who deliver earlier in gestation due to decreased mammary gland development and decreased levels of prenatal hormones necessary for preparation of the breast for lactation.

Following stratification, mothers will be randomly assigned to one of three groups to begin milk expression at different time periods following delivery. Group 1 (early expressers) will begin milk expression 0-60 minutes following delivery, Group II (intermediate expressers) will begin 61-180 minutes following delivery, and Group III (late expressers) will begin 181-360 minutes following delivery. The selection of the time periods for the groups is based upon our preliminary data showing greater milk volume and earlier lactogenesis stage II in women who began milk expression within 1 hour following delivery compared to those who began milk expression 1-6 hours following delivery (Parker et al., in press).

### Procedure

The procedures used in this study will be the same as those successfully used in our recent pilot study. Mothers will be randomized, assisted with their first mechanical milk expression session, and then asked to bring their expressed breast milk into the NICU for weighing. Additionally, mothers will be asked when they felt a sudden sensation of fullness in their breasts indicating the initiation of lactogenesis II.

### Primary Aim

The primary aim of this study is to compare over; the infant's hospitalization the effect of timing of initiation of breast milk expression on timing of lactogenesis stage II and amounts of breast milk produced during the following time periods:

- (a) early (within 1 hour of delivery),
- (b) intermediate (within 2-3 hours) and
- (c) late (within 3-6 hours).

Once mothers are randomly assigned to one of the three intervention groups, the research coordinator, the PI, or a research assistant experienced with lactation will meet with the mother at the designated time, confirm her continued consent, and assist her with her first breast pumping session using a hospital grade breast electric breast pump. Mothers who have recently delivered premature infants often take time to recover from anesthesia and may be clinically unstable. Since these mothers cannot always express their breasts independently, the above research team members will assist these mothers with milk expression. All research team members who assist mothers with the initial milk expression session will either be certified lactation consultants or have extensive training in lactation and milk expression. Assistance may range from education to actually performing the milk expressing for the mother. In the pilot study, all mothers randomized to milk expression within one hour were able to have their breasts expressed within the first hour following delivery. Since individuals assisting mothers with the initial breast expression may be required to have significant involvement in the milk expression process, they will be evaluated prior to assisting mothers and their skills will be monitored bimonthly by the research coordinator or PI to ensure that a safe and standardized procedure is used. Furthermore, a procedure checklist will be used to ensure consistent information and instruction is provided to all mothers (Appendix A). Following the initial milk expression session, mothers will receive the standard written and verbal pumping instructions provided to all of the mothers who are pumping breast milk for their infants (Appendix B). Information regarding maternal factors will be collected by a research team member (Appendix C)

Mothers will be visited in their hospital room by the research coordinator, PI, or a research assistant who has completed a formal lactation course approximately 24 hours after the initial breast pumping session to ensure they are successfully using the breast pump and to provide additional instruction if needed. Mothers will also have access to lactation services and nurses on the unit. There are currently 3 part time lactation specialists

Informed consent will be obtained prior to delivery. Table 1 (below) shows randomization/stratification of

employed in the hospital who provide services to all lactating mothers in the hospital. Lactation services are provided in the NICU upon request from the nurse or physician. This is congruent with all other breastfeeding mothers and those expressing milk for their infants in the NICU.

Mothers will be provided with a supply of pre-weighed and labeled milk vials in which they will place the milk following expression per standard NICU policy. During hospitalization or while visiting their infant in the NICU, mothers will have a hospital grade electric pump available for use. Upon discharge, all mothers will be provided the same hospital grade electric pump for use while their infant is in the NICU and they continue to lactate. Mothers will be asked to bring vials from all pumping sessions to the NICU, regardless of apparent results. While mothers are still hospitalized, the mother or nurse will bring the vials to the NICU following each expression, where they will be deposited in a refrigerator specified for storage of breast milk for all infants in the NICU. Once mothers go home, they will be instructed to store their vials of expressed breast milk in the refrigerator or freezer at home, and to bring vials to the NICU when visiting their infants (standard NICU policy). All breast milk will be weighed by a research assistant blinded to the group assignment of the mother. After milk is weighed, the milk will be available for infant consumption. Should breast milk be required for infant consumption prior to being weighed, the bedside registered nurse will remove the necessary breast milk with a syringe and record the exact amount of milk removed (mL of breast milk is equivalent to mg of breast milk). Mothers who continue milk expression will be reminded 3 times per week—through phone calls, texts or during visits to the NICU—to bring in their breast milk when they visit.

Measurement of milk volumes by weight will occur at the initial expression session, for the first 7 days, and for one 24-hour period on weekly until the infant is discharged from the hospital. (see Table 2 for a list of all instruments). If the infant breastfeeds during the 24-hour period, test weighing will be used to calculate breast milk consumed. Test weighing or the weighing of infants prior to and following breastfeeding, has been shown to be an accurate method of determining intake during breastfeeding in preterm infants (Haase, Barreira, Murphy, Mueller, & Rhodes, 2009; Hurst, Meier, & Engstrom, 2004). Prior to each breastfeeding session, infants will be weighed by the nurse assigned for patient care, and weight will include the clothing, diaper and/or blankets infant is wearing. Following completion of the breastfeeding session, the infant will be weighed again, clad in the same clothing as with initial weight. Infants will be weighed on the Baby Weigh scale (Medela, Inc, McHenry, IL) to the nearest 0.2 g. The Baby Weigh scale is a portable electronic digital scale that is accurate to within 0.2 grams. The scale will be calibrated by the study coordinator prior to initiation of the study and after every 10 measurements, using 0.2mg, 1 mg, 10mg and 50 mg weights. All weights will meet or exceed ASTM (American National Standards Institute) specifications and will be calibrated by a NVLAP (National Institute of Standards and Technology) accredited lab. The difference between the pre and post-feeding weights will be recorded on the Breastfeeding Data Collection Form taped at the infant's bedside and will be added to the total amount the mother expressed during that 24-hour period (Appendix E).

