### Sample and Setting

180 mothers who have been hospitalized anticipating delivery of an infant less than 32 weeks' gestation and weighing less than 1500 grams will be sampled by convenience from a maternity unit at Shands Teaching Hospital, a Level III tertiary care center. With a 5% anticipated drop-out rate, the final sample will include 180 mothers. The hospital is part of the University of Florida and includes a Level III (52 bed) NICU. The hospital catchment area encompasses North Central Florida and Southern Georgia, a predominantly rural and semi-rural population. 120 VLBW infants per year are delivered with 95% of these women electing to express breast milk for their infants. In our preliminary work, all but 1 mother consented for the study.

Inclusion criteria for the mothers are: 1) at least 18 years of age, 2) English speaking , 3) stated intent to breastfeed, 4) anticipating the birth of a very low birth weight infant ( $\leq 1500$  grams) between 23-32 weeks gestation. Exclusion criteria are: 1) known illicit maternal drug use, 2) history of breast reduction or augmentation, 3) positive HIV status, 4) mother not transported to recovery by 45 minutes following delivery or 5) infant not expected to live over 2 weeks following delivery.

All infants born to mothers will be included in the sample (see Targeted Enrollment Table, for Infants). Mothers delivering twins will be included since milk volume in pump dependent mothers of multiple births have been shown to be similar to mothers delivering singletons (Bishara, Dunn, Merko, & Darling, 2009). Mothers will not be approached if they have received pain medicine within the last 4 hours. Their mental and physical ability to consent will be verified with the nurse caring for them.

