#### Design/Analysis Issues.

Analysis sets. For primary analyses the intent-to-treat (ITT) sample will be used comprising all randomized mothers patients. Secondary per-protocol (completer) analysis will include mothers who were compliant with protocol requirements and for whom all required measurements have been made. ITT and per-protocol analyses will be compared to test the sensitivity of our conclusions to non-adherence/attrition.

Missing data. Every attempt will be made by the study coordinator to keep mothers in the study, with the help of the student research team members and to obtain required measurements in order to ensure the completeness of the study data. To minimize potential bias due to missing observations, mothers will be contacted by phone if vials of expressed breast milk are missed, and reasons for missing data will be carefully documented. Subject participation will only be terminated due to safety reasons for mother and infant, withdrawal of consent, or loss to follow-up. Several approaches to handle missing data in the ITT analysis set will be employed. For continuous variables using a single end-of-study value (e.g., amount of milk expressed at day 42), Little and Rubin's multiple imputation methods will be used (Little & Rubin, 1997). For analyses of longitudinal outcome data, we will use longitudinal methods (e.g. mixed models) capable of dealing with missing data (Hedeker & Gibbons, 2006).

Multiple outcome variables. In order to address possible Type I errors due to the number of outcome variables, we specify the primary outcome measures a priori corresponding to the stated a priori hypothesis and maintain the alpha (significance) level at 0.02. For analysis of secondary outcome variables, we will further adjust resulting p-values using Bonferroni-type corrections for multiple outcomes. Both unadjusted and adjusted p-values will be reported.

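### Continued consent is confirmed after assignment at a time that differs by arm, and two exclusions knowable only after birth need not be settled before allocation, so mothers can be lost at arm-dependent rates before any outcome is measured

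*Combined protocol and SAP*

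**What the plan says.** Initial consent is antenatal: "Informed consent will be obtained prior to delivery". After the birth, the Randomization section states that "mothers who continue to meet inclusion criteria will be stratified according to the gestational age of the infant", and random assignment follows. The minute at which assignment happens is not given.

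Sample and Setting lists inclusion and exclusion criteria separately. The last two exclusions are "4) mother not transported to recovery by 45 minutes following delivery or 5) infant not expected to live over 2 weeks following delivery". Neither can be known before birth. The second is a judgement, with no time by which it must be made.

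Under Primary Aim, after assignment, the coordinator, the investigator or a research assistant "will meet with the mother at the designated time, confirm her continued consent", and then helps with the first pumping session. The designated time is the arm's own window: "Group 1 (early expressers) will begin milk expression 0-60 minutes following delivery", with 61-180 minutes for Group 2 and 181-360 minutes for Group 3.

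Two sections govern what happens next:
- Design/Analysis Issues says that for primary analyses "the intent-to-treat (ITT) sample will be used comprising all randomized mothers". It limits termination of participation to three reasons: safety, withdrawal of consent and loss to follow-up.
- Potential Problems and Alternative Strategies names loss between antenatal consent and first expression as the likeliest difficulty, while judging it very improbable from the pilot. It adds that a mother who chooses to pump earlier or later than assigned reverts to usual nursing care and loses her eligibility.

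**The concern.** Randomization makes the arms comparable only if remaining in the study does not depend on the arm. Here the question of continued consent is put in the first hour to one arm and three to six hours after delivery to another, by someone who knows the assignment. The Primary Aim section itself describes these mothers as slow to recover from anesthesia and possibly unstable, so the same question may get different answers at different times. The two post-birth exclusions add a further opening, because the text does not say that they are closed before the arm is known.

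The loss would come before the first milk measurement, and before the daily lactogenesis II questioning, which starts 24 hours after delivery. A mother who leaves at that point stays in the intention-to-treat set by name but has no outcome data.

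**Working it through.** **1. Order of events.**

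| Step | Before or after assignment | Same time in all arms? |
|---|---|---|
| Antenatal consent | Before | Yes |
| Re-check of inclusion criteria after birth | Before | Yes |
| Exclusion 4, recovery by 45 minutes | Not stated | The 45 minutes fall inside Group 1's 0-60 window and before the Group 2 and 3 windows open |
| Exclusion 5, infant prognosis | Not stated | No time given |
| Continued consent | After | No: 0-60, 61-180 or 181-360 minutes |
| Loss of eligibility for pumping at another time | After | No: tied to the assigned window |

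The consent check is after assignment on any reading. For exclusions 4 and 5 the order is left open. The last row is an explicit removal rule, and its reason is not among the three termination reasons in Design/Analysis Issues.

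**2. What the analysis can do.** The plan offers mixed models for longitudinal data and multiple imputation for single end-of-study values. A mother with no measurement after assignment adds no outcome information to a mixed model. Imputing her values from baseline data assumes that, given those data, her missing outcomes resemble those observed. The trial's data cannot test that.

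**3. The plan's own power figure.** Sample Size Determination gives 60 per group, a difference of 34.1 hours, SD 55.0 hours, two-sided alpha 0.02 and 85% power. The effect is 34.1/55.0 = 0.62 SD. The noncentral t distribution gives 84.9% and the normal approximation 85.8%, so the figure reproduces. With 57 per group (5% lost in both) power is 82.7%; with 54 against 57 it is 81.5%. Lost power is the smaller issue.

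**4. Size of a shift (illustration).** From the plan: 60 per arm, SD 250 mL, target 125 mL. Assumed: n = 3 or 6 mothers lost from one arm only (5% or 10%), whose mean is D = 125 or 250 mL (0.5 or 1 SD) lower. The plan's 5% dropout is an overall figure, not split by arm.

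- If D is measured from the kept mothers, the kept mean exceeds the full-arm mean by (n/60) × D.
- If D is measured from the full arm, it does so by n/(60 − n) × D.

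| n | D (mL) | (n/60) × D | n/(60 − n) × D |
|---|---|---|---|
| 3 | 125 | 6.25 | 3/57 × 125 = 6.6 |
| 3 | 250 | 12.5 | 3/57 × 250 = 13.2 |
| 6 | 125 | 12.5 | 6/54 × 125 = 13.9 |
| 6 | 250 | 25.0 | 6/54 × 250 = 27.8 |

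The shift is about 6 to 28 mL, or 5% (6.25/125) to 22% (27.8/125) of the target. In SD units the third column runs from 0.025 to 0.10. Applied to time to lactogenesis II, that is 0.025 × 55 = 1.4 hours to 0.10 × 55 = 5.5 hours.

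**5. Effect on a pairwise test.** With no true difference, a t-test at 0.02 on the kept mothers (57 or 54 against 60) rejects about 2.1% of the time at a shift of 0.025 SD, 2.4% at 0.05 SD and 3.8% at 0.10 SD.

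**The case against.** The mention of inclusion criteria in the Randomization section may be loose wording for all eligibility criteria, and a 45-minute limit makes good sense as a screen before assignment. That is plausible. It would close the gap for the exclusions if written down, but it does not move the consent check.

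A reader might infer that the plan lets staff who know the arm exclude mothers late under exclusions 4 and 5. The text does not support that: the closed termination list gives no room for it. What remains is a silence about a mother assigned before either exclusion is settled.

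At the consent check the mother decides, not the staff, and asking again before an assisted procedure is ordinary practice. This stands. Moving the check would not prevent later withdrawals; it would remove a planned checkpoint whose timing depends on the arm.

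In the pilot, every mother assigned to the first hour was expressed in time. That lowers the loss to be expected, but does not show when exclusions were applied. Blinded milk weighing protects measurement, not selection.

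A reader might also infer that "Mothers will not be approached if they have received pain medicine within the last 4 hours" shuts out most of Group 3's window. It sits next to the check on ability to consent, and consent is antenatal, so it reads as a rule for that first approach. Even if applied after birth, medicine given at delivery would bar contact until 240 minutes: 60 of Group 3's 180 minutes, one third. This point does not rest on it.

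**Conclusion.** The concern holds as a gap in procedure that should be closed. It is certain that the consent check follows assignment at an arm-specific time. It is also certain that no section requires exclusions 4 and 5 to be settled before allocation, and that the off-time pumping rule conflicts with the termination list. That losses will differ by arm is a risk, not a documented fact.

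A reader might infer that the bias would favor Group 1, because a late transfer to recovery threatens only its window. The documents do not establish this. Nothing says the exclusion would be enforced more strictly there, and Group 3's later contact leaves more time for a withdrawal or a worsening prognosis. The direction is unknown.

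Under the assumed losses the shift is modest beside the 125 mL target, but enough at the upper end to nearly double the pairwise error rate, from 2.0% to 3.8%. Those figures depend on loss in one arm only and on a gap of 0.5 to 1 SD, neither of which the documents supply.

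**What to change.** - **Randomization:** require that all inclusion and exclusion criteria, including exclusions 4 and 5, and continued consent are confirmed and logged before the allocation is opened, at the same point after delivery for every arm. State that no mother is excluded on these criteria afterwards.
- **Primary Aim:** if the mother is asked again before pumping and declines, record it as a withdrawal. Report all losses after assignment by arm, with time and reason, and keep these mothers in the intention-to-treat set.
- **Potential Problems and Alternative Strategies:** reconcile the loss of eligibility for pumping at another time with the analysis set and the termination list in Design/Analysis Issues.

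The cost is protocol wording and a line on the enrollment checklist. There are two downsides. Less time is left before the Group 1 start: a mother reaching recovery at 45 minutes leaves 60 − 45 = 15 minutes to confirm, allocate and begin. And mothers later assigned to Groups 2 and 3 have one extra brief early contact.

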**Early Initiation of Milk Expression in Mothers of Very Low Birth Weight Infants**

**NCT 01892085**

**1/8/2014**

## PROTOCOL

### Research Design

A randomized clinical trial with three treatment arms will be conducted to determine the efficacy of alternative timing of breast milk expression (mechanical pumping) on both short and long-term breast milk supply, and Mothers who have delivered a VLBW infant prematurely will be stratified by gestational age and then randomly assigned to one of three groups and asked to mechanically pump their breasts beginning at a specific time. Timing of lactogenesis stage II will be documented, and volume of breast milk produced will be measured for the first 6 weeks following delivery.

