### **Analyses for Aim 1**

The primary efficacy outcomes are amounts of breast milk expressed over the first 7 days post-initiation; days 14, 21, 28, 35, and 42 days post-initiation and weekly, and number of days to achieve lactogenesis stage II. To examine expressed breast milk amount over time (i.e. production of breast milk immediately after initiation and subsequently, volume measured daily over the first 7 days and on days 14, 21, 28, 28, and 42 post-initiation and weekly), we will compare the longitudinal profile of milk volume expressed in the three groups over the

study period using mixed effects models (MEM) analyses. These analyses will estimate the average change in breast milk volume within each group (early vs. immediate vs. late initiation) and individual change in breast milk volume for each mother. MEM analyses allow for missing data, measurement of study subjects at different time points during the study, and time varying covariates. MEM can also take into account the effect of clustering, i.e. correlation of repeated breast milk measurements within one subject (Hedeker & Gibbons, 2006; McCulloch & Searle, 2001). The efficacy variable expressed breast milk volume (mL) will be used as the dependent variable with treatment status (early vs. intermediate vs. late initiation), time and time-by-treatment interaction and gestational group (23-27 weeks vs. 38-32 weeks) as primary independent variables. In a second step, additional covariates will be included in the models to adjust for putative predictive variables such as age, mother's weight at delivery, diagnosis of preeclampsia or diabetes, parity, birth weight, weeks of gestation, behavioral factors including skin-to-skin contact ("kangaroo care"), lactation support and mean number of pumping attempts per day. Effect modifications of covariates will be examined through inclusion of a covariate-by-treatment interaction term in the multivariable models. For example, a significant age-by-treatment interaction would suggest that the relationship between treatment and milk volume is different for older mothers compared to younger mothers. Potential key intervening variables such as behavioral factors will be further examined using mediation analysis. Further, the relationship of maternal mood with amount of breast milk will be examined by inclusion of the MAACL-R scores obtained at discharge, days 21 and 42 in the longitudinal MEM model.

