Additionally, unadjusted mean differences in volume of breast milk at day 1 through 42 will first be compared overall via one-way ANOVA (or equivalently non-parametric Kruskal-Wallis tests) between the three groups. Subsequently, pooled t-tests will be used to compare unadjusted means pairwise between the groups (using significance level  $\alpha = 0.02$  to account for multiple comparisons). Mean differences for volume of breast milk at day 1 through 42 and number of days to achieve lactogenesis stage II will be adjusted for gestational group (strata) and putative covariates such as age, mother's weight at delivery, diagnosis of preeclampsia or diabetes, parity, birth weight, weeks of gestation, behavioral factors including kangaroo care and lactation support. Mean number of pumping attempts per day will be compared for each outcome measure (as dependent variable) using a general linear model (GLM) approach for the three milk initiation groups.

Furthermore, survival distribution for time from delivery to lactogenesis stage II will be obtained for each group using the Kaplan-Meier product limit method, and will be compared using the logrank test. Cox proportional hazards regression modeling (PHM) will be used with time from delivery to lactogenesis stage II as the dependent variable, and treatment (early vs. moderate vs. late initiation) and gestational group (strata) as the primary independent variables. Additional covariates and interaction terms will be added as described above for MEM analyses.

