## **Potential Problems and Alternative Strategies**

The most likely potential problem is difficulty retaining subjects in the study between consenting prior to delivery and initial breast milk expression. Although our pilot study indicated this dropout to be highly unlikely, to minimize this problem a member of the research team will be available to the mother to help her pump the first time (at the time designated). Should she chose to pump at a different time (earlier or later), then she will receive the standard care available to her from the nursing staff and will no longer be eligible for the study.

Another problem related to retention is the continued willingness of mothers to express milk at the frequency required and for the duration of the study (at least 5 times a day until attainment of lactogenesis stage II). While this frequency may appear burdensome, these are the standard directions provided to mothers of VLBW infants receiving standard care i.e. who are not enrolled in the study.

A third potential problem is retention of the mother in the study for 6 full weeks post-delivery, when many women stop pumping due to lack of breast milk. To encourage mothers to continue trying to express their milk, each mother will be assigned to a graduate research assistant with experience involving the care of lactating women. This same student RA will contact the mother three times per week, either in person in the hospital or via telephone. The student will remind the mother to continue to pump at least 5 times per day and to bring in her breast milk with every visit. The role of student RAs in maintaining contact with mothers will decrease the likelihood of contamination of data collection procedures, since the PI or one of the co-investigators could inadvertently provide lactation consultation during the calls.

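### Volume measurement ends at infant discharge in the procedures but runs to day 42 in the analyses, so late volumes may be missing by infant maturity, with late-day tests not planned for this

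*Combined protocol and SAP*

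**What the plan says.** The combined protocol and SAP gives two windows for the primary volume outcome.

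**Hospital stay.** Primary Aim sets out to "compare over; the infant's hospitalization". Its procedures take one 24-hour volume "weekly until the infant is discharged from the hospital". The home pump is supplied "for use while their infant is in the NICU and they continue to lactate", milk is brought in when the mother visits her infant, and direct breastfeeding is captured by nurse test weighing.

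**Six weeks.** Research Design states that "volume of breast milk produced will be measured for the first 6 weeks following delivery". The power analysis assumes 13 time points ending at day 42. Analyses for Aim 1 defines the outcome as "amounts of breast milk expressed over the first 7 days post-initiation; days 14, 21, 28, 35, and 42 days post-initiation and weekly". Potential Problems and Alternative Strategies discusses "retention of the mother in the study for 6 full weeks post-delivery".

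**Analysis.** The mixed model has arm, time, their interaction and two-level gestational group as its primary terms. Weeks of gestation and birth weight are added in a second step. In addition, "unadjusted mean differences in volume of breast milk at day 1 through 42" are tested by ANOVA or Kruskal-Wallis and then by pairwise t-tests, followed by covariate-adjusted means. Design/Analysis Issues plans multiple imputation for a single end-of-study value, with day 42 volume as its example, and mixed models for longitudinal data. Infant discharge is not among the listed reasons for ending participation.

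**The concern.** Under the first window, a mother contributes a late volume only while her infant is in hospital. More mature infants tend to leave sooner, and the Randomization section itself expects production to differ with gestation. A raw comparison at day 28, 35 or 42 would then be made among mothers of less mature or sicker infants, a group defined by an event after randomization.

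Two kinds of missing value would also be mixed. Potential Problems and Alternative Strategies expects many women to stop pumping for lack of milk. A mother who stopped and a mother whose infant went home while she was producing well would both simply lack a late volume, and no analysis rule separates them.

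At stake is which population the late primary-outcome points describe and, under further conditions, whether the late arm contrasts are unbiased.

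**Working it through.** **1. The plan's own power figure.** Inputs from Sample Size Determination / Power Analysis: 60 per arm, 0.5 SD, m = 13 points, intra-class correlation 0.5, two-sided alpha 0.02, stated power 85%.

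- Variance factor for a mother's mean: (1 + 12 × 0.5)/13 = 0.538, so the effective SD is 0.734.
- Standard error of the difference: 0.734 × √(2/60) = 0.134.
- Power at alpha 0.02: Φ(0.5/0.134 − 2.326) = 92.0%.
- Power at 0.02/3 = 0.00667, for three pairwise comparisons: 84.6%, which matches the stated 85%.

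**2. Effect of losing late points on pooled power.** Same formula with fewer points for every mother:

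| Points per mother | alpha 0.02 | alpha 0.00667 |
|---|---|---|
| 13 | 92.0% | 84.6% |
| 10 (three lost) | 91.4% | 83.6% |
| 8 (all of days 14 to 42 lost) | 90.7% | 82.6% |

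Precision of the pooled comparison is not the issue.

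**3. Where the loss would fall.** Postmenstrual age is gestational age at birth plus elapsed weeks. At day 42 it is 29 to 33 weeks in the 23-27 stratum and 34 to 38 weeks in the 28-32 stratum. The documents give no length of stay. Assume discharge at 35 to 37 weeks, so that discharge day = 7 × (35 to 37 minus birth weeks), and count a point on the day of discharge as measured:

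| Birth weeks | Discharge day | Weekly points lost |
|---|---|---|
| 32 | 21 to 35 | 1 to 3 |
| 31 | 28 to 42 | 0 to 2 |
| 30 | 35 to 49 | 0 to 1 |
| 29 | 42 to 56 | 0 |
| 28 | 49 to 63 | 0 |

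The 23-27 stratum loses nothing. Days 14 and 21 are intact, day 28 loses only 32-week infants, and loss is greatest at day 42. With discharge at 34 weeks, a 32-week infant would leave at day 7 × 2 = 14 and also lose day 21. The 23-27 stratum would still be untouched. Infants must also be of very low birth weight, so those born at 31 to 32 weeks may stay longer than assumed.

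**4. Single-day tests.** Power for 0.5 SD (125 ml at SD 250) at alpha 0.02 is Φ(0.5/√(2/n) − 2.326), with n per arm observed. It is 66.0% at n = 60, 54.9% at 48, 48.6% at 42 and 34.8% at 30.

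**5. When selection biases the arm contrast.** Assume no true effect, and a correlation ρ of 0.2 to 0.4 between volume and earlier discharge. With share p still observed and c = Φ⁻¹(p), the observed mean shifts by −ρ·φ(c)/p SD. The ratio φ(c)/p is 0.350 at 80%, 0.497 at 70% and 0.798 at 50%.

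- 80% in both arms: each mean shifts by −0.07 to −0.14 SD, and the difference is 0 ml.
- 70% against 80%: (0.497 − 0.350) × ρ × 250 = 7 to 15 ml.
- 50% against 80%: (0.798 − 0.350) × ρ × 250 = 22 to 45 ml.

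The sign is against the arm with more discharges. The target difference is 125 ml.

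**The case against.** Much of the protection is already in the plan. Gestational group is a stratification factor and a first-step term in the mixed model. The raw day-by-day tests supplement that model and are followed by means adjusted for stratum, weeks of gestation and birth weight. Day 42 is the named case for multiple imputation. Reasons for missing data are to be documented, and whether the mother is still expressing is established before discharge. Neonatal staff are not told the assigned group, and no section predicts earlier discharge in any arm.

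These points stand, and they limit the concern. A reader might infer that late volumes exist only for infants still in hospital. That is one reading: Research Design and the retention plan speak of six weeks without a discharge condition, and Potential Benefits offers the pump for the whole study. A reader might also infer that every weekly test from day 14 is affected, or that nothing adjusts for maturity. The calculation and the planned adjusted means contradict both.

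What remains is narrower. The six-week wording does not say how volume is obtained once the infant has gone home. Two-level stratum leaves five weeks of gestation undivided in 28-32, where loss would concentrate. The mixed model uses each mother's earlier volumes, but its missing-at-random assumption is more credible with the likely drivers of discharge included. The second-step model that adds them also adds post-randomization behaviours, such as kangaroo care and pumping frequency, so it is not a clean substitute. No missing-data rule is clearly given for the tests at days 28 and 35, and no imputation variables are named.

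**Conclusion.** The conflict over the window is certain from the text and concerns a primary outcome. Its consequence depends on length of stay, which the documents do not give. Under the assumed 35 to 37 weeks, loss is confined to about day 28 to 42 and to the upper part of the 28-32 stratum, at 1 to 3 of five weekly points for 32-week infants and fewer below.

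The loss changes the population behind the raw late-day tests. A reader might infer that it also biases the primary comparison. The documents do not show that: bias requires discharge to differ by arm and to relate to volume. The trial expects more milk for Group 1 infants and, in time, fewer complications, so a difference is possible, but it is not stated. The illustrative bias is 0 ml with equal loss and 7 to 45 ml with the unequal shares shown, all on assumed correlations. The plan should be changed, but this is not a demonstrated flaw in the main result.

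**What to change.** 1. Reconcile Research Design, the power analysis, Primary Aim and Analyses for Aim 1. Either state how volume is obtained after discharge up to day 42, or define the outcome as volume while the infant is hospitalized and say that late points then describe a shrinking group.
2. Put weeks of gestation and birth weight in the primary mixed model, alongside the existing terms, and name them in the imputation model.
3. Base inference for days 28 to 42 on arm contrasts from that model, and label the unadjusted late-day tests descriptive.
4. Code values missing through discharge separately from stopping expression, and report the number measured by arm, stratum and day.

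Items 2 to 4 are wording and use data already planned. Item 1 is wording too, unless the sponsor chooses to collect volume after discharge, which would add fieldwork. The downside is that late-day estimates lean more on the model.
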